Appendix A. Reference Values/Toxicity Grades

Safety Laboratory Data

Treatment emergent laboratory abnormalities are defined as those which occur between the start of the first infusion of blinatumomab and the end of the treatment period.

Safety laboratory values below a distinct limit (eg, detection limit, documented as “< [limit]”) will be substituted by half of the limit and values above a distinct limit (documented as “> [limit]”) will be substituted by the limit itself for all analyses.

Grading (based on CTCAE version 4.03 or above) will be assigned to each laboratory result as detailed in [Table 14-1](#). Depending on the toxicity definition, the same result may be assigned to two gradings for deviations towards higher or lower values. In case no lower limit of normal is provided for the absolute lymphocyte, neutrophils or leukocyte counts, it will not be differentiated between grade 1 and grade 0 results for these parameters. Values not meeting any of the criteria will be assigned a grade 0.

Table 14-1. Grading of Selected Laboratory Parameters

Laboratory Parameter [Unit]	Grade 1	Grade 2	Grade 3	Grade 4
Lymphocytes [G/L]	0.8 - < LLN	0.5 - < 0.8	0.2 - < 0.5	< 0.2
Neutrophils [G/L]	1.5 - < LLN	1.0 - < 1.5	0.5 - < 1.0	< 0.5
Leukocytes [G/L]	3.0 - < LLN	2.0 - < 3.0	1.0 - < 2.0	< 1.0
Platelets [G/L]	75 - < LLN	50 - < 75	25 - < 50	< 25
Hemoglobin [g/L]*	100 - < LLN	80 - < 100	65 - < 80	< 65
Albumin [g/L]	30 - < LLN	20 - < 30	< 20	not defined
AST*	> ULN – 3*ULN	> 3*ULN – 5*ULN	> 5*ULN – 20*ULN	> 20*ULN
ALT *	> ULN – 3*ULN	> 3*ULN – 5*ULN	> 5*ULN – 20*ULN	> 20*ULN
GGT	> ULN – 2.5*ULN	>2.5*ULN – 5*ULN	> 5*ULN – 20*ULN	> 20*ULN
Bilirubin	> ULN – 1.5*ULN	>1.5*ULN – 3*ULN	> 3*ULN – 10*ULN	> 10*ULN
Fibrinogen^	%change of BL <25% or 0.75*LLN - < LLN	25%- <50% of BL or < 75*LLN – 0.5*LLN	50% - <75% of BL or < 0.5* LLN – 0.25*LLN	>= 75% of BL or < 50mg/dL or < 0.25*LLN

Page 1 of 2

Footnotes defined on the next page of the table

Table 14-1. Grading of Selected Laboratory Parameters

Laboratory Parameter [Unit]	Grade 1	Grade 2	Grade 3	Grade 4
Corrected Calcium [mmol/L]*	2.0 - < LLN	1.75 - < 2.0	1.5 - < 1.75	< 1.5
Potassium [mmol/L]*	not defined	3.0 - < LLN	2.5 - < 3.0	< 2.5
Lipase	> ULN – 1.5*ULN	> 1.5*ULN – 2.0*ULN	> 2.0*ULN – 5.0*ULN	> 5.0*ULN
Amylase	> ULN – 1.5*ULN	> 1.5*ULN – 2.0*ULN	> 2.0*ULN – 5.0*ULN	> 5.0*ULN

Page 2 of 2

BL: baseline value, LLN: Lower limit of normal, ULN: Upper limit of normal

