*: Clinical criteria from CTC AE 4.0 grading were not considered in order to assign grades

^: In case of conflicting criteria the higher grade will be assigned, % change only used when baseline is <LLN

For more details refer The **Common Terminology Criteria for Adverse Events (CTCAE)**, version 4.03 which is available at the following location:

https://evs.nci.nih.gov/ftp1/CTCAE/CTCAE_4.03_2010-06-14_QuickReference_8.5x11.pdf

Notable values for vital signs are defined according to the following table

Table 14-2. Notable Abnormalities of Vital Signs

Vital Signs	Notable Abnormalities
Pulse rate (bpm)	>120 <50
Blood pressure (mmHg)	Systolic ≥160 ≤90 Diastolic ≥105 ≤50
Weight (kg)	change from baseline ≥10% (in both directions)
Body temperature (°C)	> 39

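### SAP Table 14-1 prints the fibrinogen grade 2 ceiling as 75 × LLN instead of 0.75 × LLN, so normal values meet grade 2; its percent-of-baseline criteria also do not say that a decrease is meant

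*SAP*

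**What the plan says.** SAP Appendix A, Table 14-1, grades fibrinogen by two routes, a multiple of LLN and a percentage of baseline (BL), with an absolute limit added at grade 4:

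- Grade 1: percent "change of BL <25% or 0.75*LLN - < LLN"
- Grade 2: "25%- <50% of BL or < 75*LLN – 0.5*LLN"
- Grade 3: "50% - <75% of BL or < 0.5* LLN – 0.25*LLN"
- Grade 4: ">= 75% of BL or < 50mg/dL or < 0.25*LLN"

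The footnote to the row reads "In case of conflicting criteria the higher grade will be assigned, % change only used when baseline is <LLN". The text above the table sets the default: "Values not meeting any of the criteria will be assigned a grade 0". The same text makes the table the working specification: "Grading (based on CTCAE version 4.03 or above) will be assigned to each laboratory result as detailed in" Table 14-1.

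SAP 9.6.3 names 16 laboratory parameters for summaries and shift tables, and fibrinogen is not one of them. SAP Table 9-4 promises shift tables for selected laboratory parameters and gives only examples. Fibrinogen is collected: it is in the coagulation panel of Protocol Table 5, scheduled in Protocol Table 4.

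**The concern.** In a grading row for low values, each grade should start where the milder grade stops. Grade 2 does not. Its printed ceiling lies far above the normal range, so a normal result meets a grade 2 criterion and never reaches the grade 0 default.

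The percent criteria raise a second, weaker question. Grade 1 speaks of a percent change and grades 2 to 4 only of a percentage of baseline; none gives a direction. The footnote confines these criteria to subjects whose baseline is below LLN, the subjects in whom a rise towards normal would be a recovery.

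At stake is any fibrinogen grade programmed from this row. Normal results would carry grade 2, and a fall from normal into the true grade 1 or grade 2 range would show no shift.

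**Working it through.** **Inputs.** The four cells, the footnote and the grade 0 default come from SAP Appendix A. The documents give no fibrinogen LLN, so results are in multiples of LLN. Where mg/dL are shown, an LLN of 150 to 200 mg/dL is assumed for illustration.

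**1. Do the LLN bands join?**

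- Grade 4 ceiling 0.25 × LLN = grade 3 floor 0.25 × LLN: joins.
- Grade 3 ceiling 0.5 × LLN = grade 2 floor 0.5 × LLN: joins.
- Grade 2 ceiling 75 × LLN against grade 1 floor 0.75 × LLN: ratio 75 / 0.75 = 100. It does not join.

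As printed, grade 2 runs from 0.5 × LLN up to 75 × LLN. With the assumed LLN the ceiling is 75 × 150 = 11,250 to 75 × 200 = 15,000 mg/dL.

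**2. Grades by the LLN route, normal baseline.** The footnote switches off the percent criteria here, so their interpretation does not matter.

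| Value | As printed | With 0.75 × LLN |
|---|---|---|
| 2.0 × LLN | 2 | 0 |
| 1.5 × LLN | 2 | 0 |
| 0.8 × LLN | 2 | 1 |
| 0.6 × LLN | 2 | 2 |
| 0.4 × LLN | 3 | 3 |

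The table is the same for LLN 150, 180 and 200 mg/dL. At 0.8 × LLN both grade 1 and grade 2 are met, and the higher wins. The same holds for every value from 0.75 × LLN to LLN, so grade 1 is out of reach by this route. A fall from 1.5 to 0.6 × LLN reads as grade 2 to grade 2. A fall to 0.4 × LLN still reads as grade 3.

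**3. Percent route, baseline below LLN.** Percent change = (value − baseline) / baseline. The grades below use the corrected grade 2 ceiling, to isolate the question of direction.

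| Baseline → value (× LLN) | Change | Read as change, signed or absolute | Read as value in % of baseline | Read as decrease only |
|---|---|---|---|---|
| 0.5 → 0.875 | 0.375/0.5 = +75% | 4 | 4 (175%) | 1 |
| 0.5 → 1.1 | 0.6/0.5 = +120% | 4 | 4 (220%) | 0 |
| 0.6 → 1.1 | 0.5/0.6 = +83% | 4 | 4 (183%) | 0 |
| 0.7 → 1.1 | 0.4/0.7 = +57% | 3 | 4 (157%) | 0 |

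Read as a change, a return to exactly LLN is grade 4 when LLN / baseline ≥ 1.75, that is, when baseline is at or below 1 / 1.75 = 0.571 × LLN. Correcting the grade 2 cell does not alter the grade 3 and 4 results in this table. Only the decrease reading removes them.

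**The case against.** Four points can be made on the other side.

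- **No named output uses the row.** Fibrinogen is absent from SAP 9.6.3, and Table 9-4 names only immunoglobulins, platelets and liver parameters. This stands, and it sets the weight of the point. It does not make the row inert: Appendix A assigns grades to every laboratory result as the table details, the table also grades leukocytes, albumin, GGT and potassium, which are not among the 16 items either, and the selection in Table 9-4 is left open.
- **The slip is obvious.** Only one grade 2 band fits between its neighbours, and a programmer or the output checks in SAP 8.7 would probably catch it. That is likely, but it leaves the correction to whoever reads the row. A character lost when the PDF was read cannot be fully excluded, though the other decimals in the row survived.
- **The direction is clear from context.** Every absolute criterion in the row is on the low side, restricting percent change to low baselines makes sense for grading further falls, and the appendix sends the reader to CTCAE for more detail. This carries real weight. Against it, the row never says decrease, while the weight entry in Table 14-2 does state its direction, as "change from baseline ≥10% (in both directions").
- **Safety conclusions do not rest on it.** Investigators grade adverse events by CTCAE 4.0 (Protocol 9.2.2.1) and record grade 3 and 4 laboratory values as adverse events. This stands.

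A reader might infer that the safety report will show recoveries as life-threatening values, or nearly all subjects at grade 2. The documents do not support that: the first needs a directionless reading that the rest of the row argues against, and both need a graded fibrinogen output that the SAP does not specify by name.

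**Conclusion.** The grade 2 cell is wrong as written. The ceiling is 100 times too high, all normal values meet grade 2, and grade 1 cannot be reached by the LLN route. This does not depend on the assumed LLN or on how the percent criteria are read. The LLN cut-offs for grades 3 and 4 are sound, so severe falls are still graded correctly by that route.

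The missing direction is a wording gap and not a demonstrated misgrading. It bites only when baseline is below LLN and the programmer does not supply the word decrease; in that case large rises grade 3 or 4.

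The importance is minor. It would be wrong to infer that the primary endpoint or the study stopping rule is affected: the first is MRD negativity, and the second uses DLTs that the investigator judges related (Protocol 6.2.2), not grades from this table.

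**What to change.** In SAP Table 14-1, change the LLN part of the fibrinogen grade 2 cell to `< 0.75*LLN - 0.5*LLN`, and word the percent criterion in all four grades as a decrease from baseline. Both edits are needed, since correcting the ceiling alone leaves the direction open.

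No further condition is required. The footnote already limits the percent criteria to baselines below LLN, and any decrease from such a baseline stays below the same LLN.

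The cost is one row of the SAP. If fibrinogen is not to be graded at all, deleting the row would serve equally well.

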Appendix B. Handling of Dates, Incomplete Dates and Missing Dates

The following data will be imputed using the following algorithm:

- Adverse Events
- Concomitant Medications

Table 14-3. Imputation Rules for Partial or Missing Start Dates

Start Date		Stop Date						
		Complete: yyyymmdd		Partial: yyyymm		Partial: yyyy		missing
		< 1 st dose	≥ 1 st dose	< 1 st dose yyyymm	≥ 1 st dose yyyymm	< 1 st dose yyyy	≥ 1 st dose yyyy	
Partial: yyyymm	= 1 st dose yyyymm	2	1	2	1	n/a	1	1
	≠ 1 st dose yyyymm		2		2	2	2	2
Partial: yyyy	= 1 st dose yyyy	3	1	3	1	n/a	1	1
	≠ 1 st dose yyyy		3		3	3	3	3
Missing		4	1	4	1	4	1	1

1 = Impute the date of first dose
 2 = Impute the first of the month
 3 = Impute January 1 of the year
 4 = Impute January 1 of the stop year

Note: If the start date imputation leads to a start date that is after the stop date, then do not impute the start date.

Imputation rules for partial or missing stop dates:

[figure not shown]
Initial imputation

- For partial stop date mmyyyy, impute the last of the month.
- For partial stop date yyyy, impute December 31 of the year.
- For completely missing stop date, do not impute.
- If the stop date imputation leads to a stop date that is after the death date, then impute the stop date as the death date.
- If the stop date imputation leads to a stop date that is before the start date, then there is a data error and do not impute the stop date. (ie, set the stop date as missing).

Imputation rules for partial or missing death dates:

- If death year and month are available but day is missing:
- If mmyyyy for last contact date = mmyyyy for death date, set death date to the day after the last contact date.
- If mmyyyy for last contact date < mmyyyy for death date, set death date to the first day of the death month.
- If mmyyyy for last contact date > mmyyyy for death date, data error and do not impute.
- If both month and day are missing for death date or a death date is totally missing, do not impute.

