On and after study day 1: study day= (date - date of Study Day 1) + 1

Treatment-emergent adverse event (TEAE)

Adverse events (AEs) starting on or after first dose of protocol-specified therapy as determined by the flag indicating if the adverse event started prior to the first dose on the Adverse Events Summary CRF and up to and including 30 days after the end of protocol-specified therapy. This reporting window also applies to treatment-emergent serious adverse events (SAEs).

Treatment-emergent disease-related event

Events categorized as Disease-related Events (DREs) starting on or after first dose of blinatumomab as determined by the flag indicating if the event started prior to the first dose on the Events CRF and up to and including 30 days after the end of blinatumomab.

Disease Related Events

Subject incidence of disease related events and fatal disease related events in the blinatumomab treatment period (through the safety follow-up visit) will be tabulated by

system organ class and preferred term. Refer Protocol section 9.1.1 for more details on disease related events by their system organ class.

Triple hit

Triple hit is defined as the positive rearrangement of c-MYC, BCL2 and BCL6 as collected on the 'Disease-Specific Features on the DLBCL Disease History (COO)' eCRF page.

6. Analysis Sets

This study will define the following analysis sets for the purpose of statistical analysis: Full Analysis set, Primary analysis Set, Target Dose Analysis Set, Pre-treatment Analysis Set and Dose Limiting Toxicity (DLT) Analysis Set.

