9.6.2 Adverse Events

The Medical Dictionary for Regulatory Activities (MedDRA) version 21.1 or later will be used to code all events categorized as adverse events (AEs), disease-related events (DREs) to a system organ class and a preferred term. Treatment-emergent adverse events are events with an onset after the administration of the first dose of blinatumomab treatment through 30 days after the end of blinatumomab treatment. Adverse events of interest (EOI) categories will be based on search strategies defined by Medical Coding.

The subject incidence of adverse events will be summarized for all treatment-emergent adverse events, serious adverse events, adverse events leading to withdrawal of protocol-specified therapy, and fatal adverse events.

Subject incidence of all treatment-emergent adverse events, serious adverse events, adverse events leading to withdrawal of blinatumomab, leading to interruption of IP and fatal adverse events will be tabulated by system organ class and preferred term in descending order of frequency; similar summaries will be repeated for EOIs. Time to

onset and duration of selected EOIs (infection, neurologic events, and CRS) may also be summarized.

Any serious adverse event that occurs from enrolment through the day before the first dose of blinatumomab (during the run-in period) will be documented and summarized. This applies to all subjects who have been enrolled onto the study, regardless of whether they achieve the MRD-positive status required to start treatment with blinatumomab.

A summary of blinatumomab treatment-emergent adverse events will be tabulated by system organ class, preferred term, and worst grade.

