9.6.10 Exposure to Concomitant Medication

The number and proportion of subjects receiving concomitant medications from enrolment through the day before the first dose of blinatumomab (run-in period) and from day 1 through safety follow-up will be summarized by preferred term as coded by the World Health Organization Drug dictionary in the Full Analysis Set. In addition, the number and proportion of subjects receiving anticancer therapies during long term follow-up will be summarized by World Health Organization Drug dictionary preferred term in the Full Analysis Set.

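### Code 1 of SAP Table 14-3 sets some partial start dates to the first-dose date regardless of the pre-dose flag, which can misplace run-in SAEs and omits some undated drugs from the run-in medication summary

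*SAP*

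**What the plan says.** SAP section 8.3 sends incomplete dates of adverse events and concomitant medications to Appendix B, which says "The following data will be imputed using the following algorithm" and names those two data types. Table 14-3 then assigns a code to each combination of partial start and stop. Code 1 reads "1 = Impute the date of first dose". The only override of an imputed start is "Note: If the start date imputation leads to a start date that is after the stop date, then do not impute the start date". For ongoing records the rule is "For completely missing stop date, do not impute".

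Two summaries end the day before first dose:

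- SAEs (SAP 9.6.2): "Any serious adverse event that occurs from enrolment through the day before the first dose of blinatumomab (during the run-in period) will be documented".
- Medications (SAP 9.6.10): "The number and proportion of subjects receiving concomitant medications from enrolment through the day before the first dose of blinatumomab (run-in period").

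SAP section 5 decides treatment emergence "as determined by the flag indicating if the adverse event started prior to the first dose on the Adverse Events Summary CRF", and adds: "This reporting window also applies to treatment-emergent serious adverse events (SAEs"). SAP 9.6.2 defines the same concept by onset after first dose and does not mention the flag.

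**The concern.** Setting an unclear start to the first-dose date is a usual cautious default for treatment-emergent counts: when in doubt, the event is placed on treatment. Here the same rule also feeds two summaries of the period before treatment, and there it errs in the other direction. It also overrides information the site has given. When the site has ticked that an SAE began before first dose, the period is known even if the day is not, yet the imputed onset says otherwise.

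The run-in can last up to 24 months, and the protocol (10.4.4.1 and 10.4.4.8) and the SAP both plan to describe SAEs and medications during it. At stake is whether those tables are complete, and whether an SAE recorded as pre-dose is reported in the right period.

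**Working it through.** **Inputs.** Table 14-3 with its stop-date rules and Note (SAP Appendix B); the run-in windows (SAP 9.6.2, 9.6.10); the flag rule (SAP section 5). SAEs are collected from informed consent (protocol 9.2.2.2), non-serious adverse events and disease-related events only from first dose (protocol 9.2.2.1, 9.2.1). Medication fields include start and stop dates but no pre-dose indicator (protocol 6.5).

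**Where code 1 applies.** The table has 5 start rows and 7 stop columns: 5 × 7 = 35 cells, less 2 marked not applicable = 33 (blank cells read as carrying the value above them). Code 1 fills 4 cells in each of three rows (start month equal to first-dose month, start year equal to first-dose year, start missing): 3 × 4 = 12 of 33.

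**Why the Note does not help.** In those 12 cells the stop is missing and stays missing, or is on or after first dose to its known precision. A partial stop is completed to the end of its month or year. The imputed start therefore never exceeds the stop, and the Note is never triggered.

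**Worked records.** Assumed dates: enrolment 10 Jan 2019, first dose 16 Sep 2019, so the run-in window closes on 15 Sep.

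| Record (true start) | Start recorded | Stop recorded | Code | Imputed start | In run-in window |
|---|---|---|---|---|---|
| Drug (Feb 2019) | 2019 | ongoing | 1 | 16 Sep 2019 | no |
| Drug (Feb 2019) | 2019 | 20 Oct 2019 | 1 | 16 Sep 2019 | no |
| Drug (before first dose) | missing | ongoing | 1 | 16 Sep 2019 | no |
| SAE (4 Sep), flagged pre-dose | Sep 2019 | 20 Sep 2019 | 1 | 16 Sep 2019 | no |
| SAE (4 Sep), flagged pre-dose | Sep 2019 | Sep 2019 | 1 | 16 Sep 2019 | no |
| Drug (Mar 2019) | Mar 2019 | ongoing | 2 | 1 Mar 2019 | yes |
| Drug (Feb 2019) | 2019 | 30 May 2019 | 3 | 1 Jan 2019 | yes |
| SAE (4 Sep), flagged pre-dose | Sep 2019 | 10 Sep 2019 | 2 | 1 Sep 2019 | yes |

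**What happens to the two moved SAEs.**

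- Onset date decides both tables (9.6.2 alone): counted as treatment-emergent, against the flag.
- Flag decides both: counted in run-in, correctly.
- Flag decides treatment emergence (section 5) and imputed date decides run-in (9.6.2): counted in neither.

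The SAP does not say which combination applies.

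**Size, given a true run-in start and a record still ongoing at first dose.** Let L be the run-in length in months and U the length of the known calendar unit (1 for month, 12 for year). Assume starts uniform over the run-in and first dose uniform within the unit. The share moved is U/(2L) when L ≥ U, and 1 − L/(2U) when L < U.

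- Month known, L = 3, 6, 12, 24: 1/6, 1/12, 1/24, 1/48 = 16.7%, 8.3%, 4.2%, 2.1%. Simulating whole-day dates gives 16.0%, 8.2%, 3.9%, 1.9%; the formula runs slightly high because a run-in start must be at least one whole day before first dose.
- Year only: 1 − 3/24, 1 − 6/24, 1 − 12/24, 12/48 = 87.5%, 75%, 50%, 25%. Simulation: 87.2%, 74.9%, 50.0%, 25.1%.
- Start missing: 100%.

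**The case against.** **SAEs.** It can fairly be said that no passage tells the analyst to mix the flag with the imputed date. If the flag is used throughout, the SAE is in run-in. Section 5 makes the flag decisive, and the sample SAE form in protocol Appendix B has a tick-box for events before first dose. A reader might infer that flagged SAEs will certainly vanish from both tables; the documents do not support that, only that it can happen. What stands is that 9.6.2 does not mention the flag, and that two of the three readings give a wrong result.

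**Breadth.** A reader might also infer that every partly dated run-in record is moved. It is not. A stop before first dose, or a known start month or year different from that of first dose, leads to codes 2 to 4 and a start before treatment. Among events, only SAEs are at issue.

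**Size.** The 100% for missing starts is conditional on a true pre-dose start. It is not an error rate among all partly dated records, because those that really began on treatment are left out. SAEs must reach the sponsor within 24 hours of awareness and data issues go for resolution before lock (SAP 8.1), so partial SAE dates should be few.

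**Remedy for medications.** Any rule for an unknown start will misplace some drugs. For month-only starts, changing the code gains nothing: with first dose on 16 Sep, 15 days of the month fall before it and 15 on or after, so moving all such records to 1 Sep merely swaps one misclassification for another. This stands, and month-only medication starts are best left alone.

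**Conclusion.** The point holds for the code-1 cells. The table imputes an onset that can contradict a recorded pre-dose flag. For medications no indicator is listed that could correct the result, so an ongoing drug with a missing start, or a year-only start in the first-dose year, is excluded by rule from the run-in summary. It is still counted from day 1 through safety follow-up.

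The effect is small. Only descriptive safety tables in treated subjects are touched; the MRD endpoint and the other efficacy results are not. The documents do not say how many dates are partial, so no count of affected records can be given, and the shares above rest on uniform start and first-dose dates. A claim that treatment-emergent counts are distorted in general would go too far: for unflagged events the first-dose default is a sound cautious choice and should stay.

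**What to change.** In SAP Appendix B and 9.6.2:

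- **Flagged events.** If the CRF flag says the event began before first dose, do not use code 1. Impute the first of the known month, or January 1 of the known year, never later than the day before first dose. If the start is wholly missing, that limit can itself serve as the date.
- **Run-in SAE table.** Define it by the pre-dose flag, and name the flag as decisive for treatment emergence in 9.6.2 as in section 5, so that each SAE falls in exactly one of the two periods. An imputed date should not decide membership at the enrolment end either, since the first of a month or January 1 can precede enrolment. SAEs in enrolled subjects who are never treated, whom 9.6.2 already includes, all belong in this table.
- **Medications.** Where code 1 would move a drug with a missing or year-only start, count it in both the run-in and the on-treatment summaries unless the record shows that it began on treatment. Leave month-only starts as they are.

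The cost is a few lines of SAP text and a small programming change, with no new data. The downside is that some undated drugs that really began on treatment will also be counted in run-in; a table footnote should say so.
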